4.5.2 Pharmacokinetic (Secondary)

N/A

4.6 Analysis of Safety

All safety data will be reported for the Safety Population as per actual study product received. The safety profile of the study products will be assessed with respect to adverse events (AEs).

4.6.1 Adverse Events and Serious Adverse Events

All AEs will be reviewed by the Clinical Research Scientist or Designee prior to database lock and will be coded to a system organ class (SOC) and preferred term (PT) using the Medical Dictionary for Regulatory Activities (MedDRA).

AEs will be classified as Skin (Face/Non-Face) and non-skin on the AE page of eCRF.

Treatment emergent adverse events (TEAEs) are defined as new AEs that occur on or after the first treatment application (if this date is missing a suitable alternative will be used eg date of

randomization). Adverse events with an onset date/time prior to the first study product application will be considered as non-treatment emergent.

The following summary tables and listings will be presented by treatment.

- Table of TEAEs by SOC and PT (PPD [REDACTED]).
- Table of TEAEs by Skin(Face/Non-Face)/Non-Skin and PT (PPD [REDACTED])
- Table of TEAEs by SOC, PT and severity (PPD [REDACTED])
- Table of treatment-related TEAEs by SOC and PT (PPD [REDACTED])
- Table of treatment-related TEAEs by Skin(Face/Non-Face)/Non-Skin and PT (PPD [REDACTED])
- Table of treatment-related TEAEs by SOC, PT and severity (PPD [REDACTED])
- Table of treatment-related serious adverse events (SAEs) by SOC and PT (PPD [REDACTED]) [only produced if there are more than 5 SAEs]
- Table of AEs related to COVID-19 by SOC and PT (PPD [REDACTED])
- Listing of all AEs (PPD [REDACTED] for all randomized subjects; PPD [REDACTED] for non-randomized subjects)
- Listing of all AEs related to COVID-19 Subjects (PPD [REDACTED] for all screened subjects)
- Listing of deaths (PPD [REDACTED])
- Listing of non-fatal SAEs (PPD [REDACTED])
- Listing of TEAEs leading to study product discontinuation (PPD [REDACTED])
- Listing of TEAEs classified as skin(Face/Non-Face) (PPD [REDACTED])

In the event that there is nothing to report, a null table or listing will be produced.

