The first application of the assigned study product will be at the investigational site under the supervision of a trained technician. Subjects will be instructed self-assess the signs and symptoms of cutaneous and ocular irritation they are currently experiencing 1-2 hours after first product application.

Visit 1 and Visit 2 may be combined. If Visit 1 and 2 are not combined, Visit 2 must occur within 7 calendar days of Visit 1. If Visits 1 and 2 are combined, the baseline dermatologist and ophthalmologist assessments and subject self-assessment of cutaneous and ocular irritation will occur before the LAST and any product application. The LAST will be completed at least 30 minutes prior to first product application.

Subjects will be instructed to apply their assigned study product at home again the same evening of their first supervised application and then twice-daily for a total of 21 (+2) days as part of their normal skin care routine. A paper diary will be provided to each subject to record the number of daily applications of product, from first application at site to final application at home. Subjects may also record additional information such as AEs or medications used during the home use period in the provided diary.

The final application of product will be at home on the morning of the final visit (Visit 3).

At Visit 3 (final visit), the dermatologist and ophthalmologist will conduct final assessments of the signs and symptoms of cutaneous and ocular irritation, respectively.

A total dermatologist score will be calculated as the sum of the erythema, dryness, scaling and edema scores for the baseline visit and final visit. The dermatologist will determine whether any subject with an increase in total dermatologist score at final visit versus baseline experienced a clinically relevant positive reaction, or not. Similarly, a total ophthalmologist score will be calculated as the sum of the eczema of the eyelid, conjunctivitis, follicles and chemosis conjunctivae scores for the baseline visit and final visit. The ophthalmologist will determine whether any subject with an increase in total ophthalmologist score at final visit versus baseline experienced a clinically relevant positive reaction, or not.

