10.1 Definition of an Adverse Event (AE)

An AE is any untoward medical occurrence in a clinical study subject, temporally associated with the use of a study product including any washout or lead-in product (or medical device),

whether or not considered related to the study product, including any washout or lead-in product (or medical device).

NOTE: An AE can therefore be any unfavorable and unintended sign (including an abnormal laboratory finding), symptom, or disease (new or exacerbated) temporally associated with the use of a study product including any washout or lead-in product (or medical device).

Events Meeting the AE Definition:

- Any abnormal laboratory test results (hematology, clinical chemistry, or urinalysis) or other safety assessments (e.g. ECG, radiological scans, vital sign measurements), including those that worsen from baseline, considered clinically significant in the medical and scientific judgment of the investigator (i.e., not related to progression of underlying disease).
- Exacerbation of a chronic or intermittent pre-existing condition including either an increase in frequency and/or intensity of the condition.
- New conditions detected or diagnosed after study product administration even though it may have been present before the start of the study.
- Signs, symptoms, or the clinical sequelae of a suspected drug-drug interaction.
- Signs, symptoms, or the clinical sequelae of a suspected overdose of either study product or a concomitant medication. Overdose per se will not be reported as an AE/SAE unless it is an intentional overdose taken with possible suicidal/self-harming intent. Such overdoses should be reported regardless of sequelae.

Events NOT meeting the AE definition:

- Any clinically significant abnormal laboratory findings (if applicable) or other abnormal safety assessments which are associated with the underlying disease, unless judged by the investigator to be more severe than expected for the subject's condition.
- The disease/disorder being studied or expected progression, signs, or symptoms of the disease/disorder being studied, unless more severe than expected for the subject's condition.
- Medical or surgical procedure (e.g. endoscopy, appendectomy) is not the AE. The condition that leads to the procedure is an AE (e.g. appendicitis).
- Situations where an untoward medical occurrence did not occur (social and/or convenience admission to a hospital).

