- Anticipated day-to-day fluctuations of pre-existing disease(s) or condition(s) present or detected at the start of the study that do not worsen.
- Any observed response to the LAST that can be denoted according to the score of the reactions (per [Table 8-1 Lactic Acid Sting Test Score](#)) will not be considered an adverse event. Only in the case of unusual reactions, in the opinion of the qualified dermatologist, will these reactions and the consequences observed upon evaluation be documented as AE's.
- Any observed cutaneous or ocular response that can be denoted according to the grade of the reactions (per [Safety and Other Assessments](#)) will not be considered an adverse event. Only in the case of unusual reactions, in the opinion of the clinical expert, will these reactions and the consequences observed upon evaluation be documented as AEs.

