10.3 Time Period and Frequency for Collecting AE and SAE Information

All AEs, and therefore all SAEs will be collected immediately after a subject provides consent to participate in the study by the completion (signature) of the ICF and until 5 days following last administration of the study product (or last procedure).

Medical occurrences that began before obtaining informed consent will be recorded in the Medical History/Current Medical Conditions section of the CRF not the AE section.

Details recorded by the subject on a diary or similar document that meet the definition of an AE must also be discussed with the subjects and transcribed in the AE section of the CRF.

All SAEs will be recorded and reported to the sponsor or designee immediately and under no circumstance should this exceed 24 hours. The investigator will submit any updated SAE data to the sponsor within 24 hours of it being available.

Investigators are not obligated to actively seek AEs or SAEs after the conclusion of the study participation. However, if the investigator learns of any SAE, including a death, at any time after a subject has been discharged from the study, and he/she considers the event to be reasonably related to the study product or study participation, the investigator must promptly notify the sponsor.

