10.6 Follow-up of AEs and SAEs

After the initial AE/SAE report, the investigator is required to proactively follow up with each subject and provide further information on the subject's condition.

All AEs (serious and non-serious) will be followed until resolution, until the condition stabilizes, until the event is otherwise explained, or until the subject is lost to follow-up.

The investigator is obligated to perform or arrange for the conduct of supplemental measurements and/or evaluations as may be indicated or as requested by GSK CH to elucidate as fully as possible the nature and/or causality of the AE. This may include additional laboratory tests or investigations, histopathological examinations, or consultation with other health care professionals.

New or updated information will be recorded on the AE CRF page and on the SAE form (subject to the classification of the AE).

The investigator will submit any updated SAE data to GSK CH within 24 hours of receipt of the information.

Investigators are not obliged to actively seek AEs in former subjects. However, if the investigator learns of a SAE, including death, at any time after a subject has been discharged from the study, and considers the event reasonably related to the study product or study participation, the investigator will promptly notify GSK CH by emailing the information to the GSK CH Clinical Operations Safety Reporting email box (PPD [REDACTED]). The GSK CH Study Manager or designee will be responsible for forwarding the information to the Case Management Group, Global Clinical Safety and Pharmacovigilance group mailbox at GSK (PPD [REDACTED]).

The investigator will submit any updated SAE data to GSK CH within the designated reporting time frames.

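### SAP 4.6.1 has no rule for an AE that starts before first application and worsens on product, and its discontinuation output is narrower than protocol 12.3.3 without the change being declared

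*SAP*

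**What the plan says.** SAP 4.6.1 gives the definition: "Treatment emergent adverse events (TEAEs) are defined as new AEs that occur on or after the first treatment application". It then closes off earlier onsets: "Adverse events with an onset date/time prior to the first study product application will be considered as non-treatment emergent". Neither sentence mentions worsening.

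The protocol opens AE collection earlier than that cut-off. Section 10.3 states: "All AEs, and therefore all SAEs will be collected immediately after a subject provides consent to participate in the study". Section 10.1 includes among AEs: "Exacerbation of a chronic or intermittent pre-existing condition including either an increase in frequency and/or intensity of the condition". On later changes to an AE already reported, section 10.6 says: "New or updated information will be recorded on the AE CRF page and on the SAE form" (the latter where the event is serious). No section says whether worsening of an open AE gets a new record with its own onset.

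For discontinuations, protocol 12.3.3 plans summaries for each test product of treatment-emergent AEs, treatment-related AEs, AEs leading to discontinuation and serious AEs. The TEAE limit attaches only to the first of these. SAP 4.6.1 provides a listing, restricted to TEAEs, of events leading to product discontinuation. SAP Table 5-1, which is meant to set out departures from the protocol's analysis, covers the prior and concomitant medication definitions, the population for their listing, and the COVID-19 safety outputs. It does not mention this restriction.

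**The concern.** The safety endpoint is the frequency and severity of AEs. If emergence depends only on the first onset date, a reaction that is trivial before the product and marked after it is reported as if the product had no part in it. The error can run only one way, because the rule can remove an event from a product's tables but cannot add one.

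The AE tables also carry a particular load here. Gradable skin and eye irritation is handled by the scores and is kept out of AE reporting, so the AE tables mainly show what the scales do not capture. Losing one of those events because of its start date is a loss of the information the tables are there to give.

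**Working it through.** No design figure bears on this point. The plan's one probability statement reproduces (45 per arm, 4% incidence: P(X ≤ 4) = 0.9668; 0.9668³ = 0.9037) and is unchanged by anything below.

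**Step 1: can an AE precede first application?** Yes. Collection starts at consent. If Visits 1 and 2 are combined, consent and first application fall on the same day. If not, Visit 2 is within 7 calendar days of Visit 1. A facial irritant test falls in this interval: "The LAST will be completed at least 30 minutes prior to first product application".

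**Step 2: which events qualify?** Protocol 10.1 lists as not being an AE: "Any observed response to the LAST that can be denoted according to the score of the reactions". The same section excludes cutaneous and ocular responses that fit the grading scales. What remains is an unusual LAST reaction, or any other non-gradable event of the screening period.

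**Step 3: how is worsening recorded?** Two routes are open.
- Same record updated, as 10.6 can be read: onset stays before first application, so the event is non-treatment-emergent whatever its later intensity.
- New record opened, as 10.1 would allow for an exacerbation: onset is on or after first application, so it is a TEAE.

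The documents do not choose between them. By contrast, a condition that began before consent is medical history under 10.3. Its exacerbation on product can be entered as an AE with on-product onset, and so is a TEAE. A condition that began after consent and worsened identically can be classed the other way.

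**Step 4: where does an event on the first route appear?** Outputs in SAP 4.6.1:

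| Output | Event included? |
|---|---|
| TEAEs by SOC/PT, by skin class, by severity (3 tables) | No |
| Treatment-related TEAEs, same three layouts (3 tables) | No |
| Listing of skin TEAEs | No |
| Listing of TEAEs leading to product discontinuation | No |
| Treatment-related SAE table (only if more than 5 SAEs) | Yes, if serious and related |
| COVID-19 AE table and listing | Yes, if COVID-19-related |
| Listings of deaths and of non-fatal SAEs | Yes, if serious |
| Listing of all AEs, randomized subjects | Yes |

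So 6 of 8 AE tables omit it by definition. The related-event tables, skin listing and discontinuation listing matter only if the event is related, on the skin, or led to stopping.

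**Step 5: scale.** About 150 randomized over 3 arms is 150/3 = 50 per arm, and the plan requires 45 completers per arm. One omitted subject changes an arm's AE incidence by 1/50 = 2.0 or 1/45 = 2.2 percentage points. The number of such subjects is not given.

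**Step 6: discontinuations.** Compared with protocol 12.3.3, the SAP output differs in being limited to TEAEs and in being a listing rather than a summary. Both differences exist however worsening is recorded.

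**The case against.** The strongest reply is that the gap is narrow and may never show. The window is about a week at most. Expected LAST reactions and gradable irritation are not AEs, and on the separate-visit path exclusion criteria 18 to 23 are applied after the LAST and before randomization. Aggravated facial irritation is what the primary endpoint measures, through the score increase and the dermatologist's judgement. A site may also record the worsening as a new AE, which removes the problem. If the subject withdraws, SAP 4.1.1 tabulates discontinuation by reason and product. All of this stands, and it limits frequency. It does not supply the missing rule, and it does not touch the mismatch on discontinuations.

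A reader might infer more than the documents support:
- That the event vanishes from every product AE table. It does not: the treatment-related SAE and COVID-19 tables are not TEAE-limited, and the all-AE listing retains the event.
- That the LAST makes pre-product facial AEs likely, with mild erythema after the test as the typical case. The protocol excludes responses that fit the LAST score, and erythema is a graded attribute, so mild erythema would not ordinarily be an AE at all.
- That the SAP contradicts protocol 10.1. That section defines an AE, not treatment emergence. The SAP simply leaves the classification of a worsened AE to recording practice.

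**Conclusion.** The point holds in limited form. SAP 4.6.1 states an onset-only rule that can misclassify a non-gradable AE that opens between consent and first application, worsens on product and is kept under its original onset date. Such an event is missing from all six TEAE tables and from the skin and discontinuation listings. It is still visible in the all-AE listing and, if serious, in the death or SAE listing. Few events should be affected, and the primary and secondary endpoints, which rest on scores, are not.

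The conclusion assumes that the worsening is not entered as a new AE. CRF completion instructions, which might settle this, are not among the documents.

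The undeclared narrowing of the discontinuation output needs no such assumption. It is a plain difference between protocol 12.3.3 and SAP 4.6.1 that Table 5-1 does not report. Together these justify a cheap improvement; they do not threaten the study's main conclusion.

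**What to change.** In SAP 4.6.1, define a TEAE as an AE with onset on or after first application, or one with earlier onset that increases in intensity or becomes serious on or after first application. Instruct the site to enter such worsening as a separate AE record with the date and time of worsening, so that the tables use the on-product intensity.

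Replace the TEAE-limited discontinuation listing with output based on all AEs leading to discontinuation, summarised by product as protocol 12.3.3 has it.

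The cost is SAP wording, one CRF completion instruction and minor programming. The downside is small: a few LAST-related events may appear under a product, with the investigator's causality assessment alongside.

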4.6.2 Other Safety Variables

Other safety variables are listed below:

- COVID-19 infection diagnosis and assessment
- COVID-19 infection diagnosis and assessment – symptoms for symptomatic subjects

COVID-19 diagnosis and assessment and the symptoms for symptomatic subjects data will be listed (PPD [REDACTED] and PPD [REDACTED], respectively) for all screened subjects.

4.7 Analysis of Other Variables

No other analyses will be performed for this study.

5 Changes to the Protocol Defined Statistical Analysis Plan

Any changes from the originally planned statistical analysis specified in the protocol are outlined in [Table 5-1](#).

Table 5-1 Changes to Protocol Defined Analysis Plan

Protocol	Reporting & Analysis Plan	
Statistical Analysis section	Statistical Analysis Plan	Rationale for Changes

 Section 6.8: Medication/treatments taken within 30 days of signing the informed consent form will be documented as a prior medication/treatment. Medications/treatments taken after the first supervised test product application (serum, lotion or cream) will be documented as concomitant medication/treatments. Section 12.3.7: Prior medications, concomitant medications and significant non-drug therapies taken during treatment will be listed for the safety population. N/A 	
 The current standard definition of the prior medication and concomitant medications has been used in the Reporting and Analysis plan. Prior medications are defined as those, which stopped before the first application of the study product. Concomitant medications are defined as the medication ongoing or started on or after the first application of the study product. Prior medications, concomitant medications and concomitant non-drug treatments/procedures taken during treatment will be listed for the Randomized population. Section 4.6: Safety analysis for COVID subjects added 	
 To maintain the current standard definition of prior medication and concomitant medications Importantly, all medications/therapies concomitant to study participation will be provided. To maintain the current listing presentation This is not part of the protocol and covered under RAP

Attachment 1: List of Data Displays

PPD
